10.4. Criteria for Potentially Clinically Significant Values (PCSV)

Parameter	PCSV
Clinical chemistry	
ALT	By distribution analysis: >2 ULN and baseline \leq 2 ULN >3 ULN and baseline \leq 3 ULN >5 ULN and baseline \leq 5 ULN >10 ULN and baseline \leq 10 ULN >20 ULN and baseline \leq 20 ULN
AST	By distribution analysis: >2 ULN and baseline \leq 2 ULN >3 ULN and baseline \leq 3 ULN >5 ULN and baseline \leq 5 ULN >10 ULN and baseline \leq 10 ULN >20 ULN and baseline \leq 20 ULN
Alkaline Phosphatase	> 1.5 ULN and baseline \leq 1.5 ULN
Total Bilirubin	> 1.5 ULN and baseline \leq 1.5 ULN > 2 ULN and baseline \leq 2 ULN
Conjugated bilirubin	> 35% total bilirubin (when total bilirubin >1.5 ULN)
ALT and Total Bilirubin	ALT > 3 ULN and Total Bilirubin > 2 ULN and baseline ALT \leq 3 ULN or Total bilirubin \leq 2 ULN
CPK	> 3 ULN and \leq 5 ULN and baseline \leq 3ULN >5 ULN and \leq 10 ULN and baseline \leq 5 ULN >10 ULN and baseline \leq 10 ULN
Creatinine	\geq 150 μ mol/L (adults) \geq 30% from baseline \geq 100% from baseline
CLcr (mL/min) (Estimated creatinine clearance based on the Cockcroft-Gault equation)	\geq 15 - <30 (severe decrease in GFR) \geq 30 - < 60 (moderate decrease in GFR) \geq 60 - <90 (mild decrease in GFR) \geq 90 (normal GFR)
eGFR (mL/min/1.73m ²) (Estimate of GFR based on an MDRD equation)	\geq 15 - <30 (severe decrease in GFR) \geq 30 - < 60 (moderate decrease in GFR) \geq 60 - <90 (mild decrease in GFR) \geq 90 (normal GFR)

Parameter	PCSV
Uric Acid Hyperuricemia: Hypouricemia:	>408 µmol/L <120 µmol/L
Blood Urea Nitrogen	≥17 mmol/L
Chloride	<80 mmol/L >115 mmol/L
Sodium	≤129 mmol/L ≥ 160 mmol/L
Potassium	< 3 mmol/L ≥ 5.5 mmol/L
Glucose Hypoglycaemia Hyperglycaemia	≤ 3.9 mmol/L and < LLN ≥ 7 mmol/L (fasted); ≥ 11.1 mmol/L (unfasted)
HbA1c	>8%
Albumin	≤25 g/L
CRP	> 2 ULN or >10 mg/L, if ULN not provided
Hematology	
WBC	< 3.0 Giga/L (3000/ mm ³) (Non-Black) < 2.0 Giga/L (2000/ mm ³) (Black) ≥16.0 Giga/L (16000/ mm ³)
Lymphocytes	>4.0 Giga/L
Neutrophils	< 1.5 Giga/L (1500/ mm ³) (Non-Black) < 1.0 Giga/L (1000/ mm ³) (Black)
Monocytes	>0.7 Giga/L
Eosinophils	> 0.5 Giga/L (500/ mm ³) or > ULN if ULN ≥ 0.5 Giga/L
Hemoglobin	≤115 g/L (Male); ≤95 g/L (Female) ≥185 g/L (Male); ≥165 g/L (Female) Decrease from Baseline ≥15 g/L Decrease from Baseline ≥20 g/L
Hematocrit	≤0.37 v/v (Male) ; ≤0.32 v/v (Female) ≥0.55 v/v (Male) ; ≥0.5 v/v (Female)
RBC	≥6 Tera/L

Parameter	PCSV
Platelets	< 100 Giga/L (100 000/mm ³) ≥700 Giga/L (700000/mm ³)
Urinalysis	
pH	≤4.6 ≥8
Vital signs	
HR	≤ 50 bpm and decrease from baseline ≥ 20 bpm ≥ 120 bpm and increase from baseline ≥ 20 bpm
SBP	≤ 95 mmHg and decrease from baseline ≥ 20 mmHg ≥ 160 mmHg and increase from baseline ≥ 20 mmHg
DBP	Young and elderly patients ≤ 45 mmHg and decrease from baseline ≥ 10 mmHg ≥ 110 mmHg and increase from baseline ≥ 10 mmHg
Orthostatic Hypotension	SBP St – Su ≤ - 20 mmHg DBP St – Su ≤ - 10 mmHg
Weight	≥5% increase versus baseline ≥5% decrease versus baseline
ECG parameters	
HR	≤ 50 bpm and decrease from baseline ≥ 20 bpm ≥ 120 bpm and increase from baseline ≥ 20 bpm
PR	≥220 ms and increase from baseline ≥20 ms
QRS	≥ 120 ms
QTc Borderline Prolonged* Additional	Absolute values (ms) Borderline 431-450 ms (Male) 451-470 ms (Female) Prolonged* > 450 ms (Male) > 470 ms (Female) QTc ≥500 ms Increase versus baseline (Males and Females) Borderline Δ 30-60 ms Prolonged * Δ > 60 ms

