 - Investigator or any sub-investigator, pharmacist, study coordinator, other study staff or relative thereof directly involved in the conduct of the protocol, etc.
 - Presence of any other conditions (eg, geographic or social), either actual or anticipated, that the investigator feels would restrict or limit the patient's participation for the duration of the study
12. Laboratory findings during screening period (not including randomization labs):
- Triglycerides >400 mg/dL (>4.52 mmol/L) for patients without a known history of diabetes mellitus (1 repeat lab is allowed);
OR
Triglycerides >300 mg/dL (>3.39 mmol/L) for patients with a known history of diabetes mellitus (1 repeat lab is allowed)
 - Positive test for Hepatitis B surface antigen and/or Hepatitis C antibody (associated with a positive HCV ribonucleic acid [RNA] polymerase chain reaction)
 - Positive serum beta-human chorionic gonadotropin or urine pregnancy test in women of childbearing potential
 - Estimated glomerular filtration rate <30 mL/min/1.73 m² according to 4-variable MDRD study equation (calculated by central lab)
 - TSH >1.5 x upper limit of normal (ULN) (1 repeat lab is allowed) for patients not on thyroid replacement therapy
 - Alanine aminotransferase (ALT) or aspartate aminotransferase (AST) > 2 x ULN at screening (1 repeat lab is allowed)
 - Creatine phosphokinase (CPK) > 3 x ULN at screening (1 repeat lab is allowed)
13. Systolic blood pressure > 160 mmHg or diastolic blood pressure > 100 mmHg at the screening visit or time of randomization (1 repeat allowed)
14. History of heart failure (New York Heart Association [NYHA] Class III-IV) within 12 months before screening

15. History of MI, unstable angina leading to hospitalization, CABG surgery, PCI, uncontrolled cardiac arrhythmia, carotid surgery or stenting, stroke, TIA, carotid revascularization, endovascular procedure or surgical intervention for peripheral vascular disease within 3 months prior screening
16. Having received LDL apheresis within 2 months before screening
17. Evidence of clinically significant intestinal malabsorption, or a history of ileal bypass, gastric bypass, or other bariatric surgery within 12 months before screening
18. Unstable weight (variation > 5 kg) within 2 months prior to screening visit

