5.8. Analysis of Safety Data

In general, for the double-blind period, the summary of safety results for patients in the double-blind SAF population will be presented by route of administration (Group A or Group B) and pooling the evinacumab dose regimens within each route of administration (Group A or Group B), with the intent to maximize efforts to identify potential safety signals. The treatment group data (individual evinacumab dose regimens and placebo) will also be presented with the intent to support the pooled dose regimens. No formal inferential testing will be performed. Summaries will be descriptive in nature.

For Group B, summaries of safety results for the open-label period will be presented for patients in the open-label SAF, by the total number of patients administered open-label study treatment (i.e., 15 mg/kg IV), as well as by the patient subgroups of study treatment received in the DBTP (i.e., 5 mg/kg IV, 15 mg/kg IV, or placebo). Summaries will be descriptive in nature.

General common rules

All safety analyses will be performed, unless otherwise specified, using the following common rules:

- For DBTP, safety data in patients who do not belong to the double-blind safety analysis set (i.e., exposed but not randomized) will be listed separately.
- PCSV values are defined as abnormal values considered medically important by the Sponsor according to predefined criteria/thresholds based on literature review and defined by the Sponsor for clinical laboratory tests and vital signs (PCSV version dated January 2009 [[Appendix 10.4](#)]). Considering that the threshold defined in the PCSV list for monocytes and basophils can be below the ULN, the following PCSV criterion will be used for the PCSV analysis of monocytes and basophils:
 - PCSV criterion for monocytes: >0.7 Giga/L or $>ULN$ (if $ULN \geq 0.7$ Giga/L).
 - PCSV criterion for basophils: >0.1 Giga/L or $>ULN$ (if $ULN \geq 0.1$ Giga/L).
- PCSV criteria will determine which patients had at least 1 PCSV during the respective TEAE periods, taking into account all evaluations including unscheduled or repeated evaluations.
- The treatment-emergent PCSV denominator by treatment group for a given parameter will be based on the number of patients assessed for that given parameter at least once during the respective TEAE periods.

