5.8.3. Clinical Laboratory Measurements

The following definitions will be applied to laboratory parameters:

- Double-blind treatment period: The treatment period used for quantitative analysis in the double-blind period is defined as the day after the first study drug administration to the day of the last double-blind study drug injection + 7 days for Group A. For Group B, the treatment period is defined from the day after the first administration of double-blind study treatment to the day of the last administration of double-blind study treatment + 28 days for those patients not proceeding into the open-label treatment period, or up to the day of the first open-label study treatment administration for those patients proceeding into the open-label treatment period.
- Open-label treatment period: The treatment period used for quantitative analysis in the open-label study period is defined from the day after the first dose of open-label study treatment to the day of the last dose of open label study treatment + 28 days.

For respective treatment period (DBTP and OLTP), clinical laboratory parameter actual values (quantitative) and change from baseline values will be descriptively summarized at baseline and each post-baseline visit by at least patient number, mean, median, Q1, Q3, SD, minimum and maximum. Clinical laboratory parameters mean changes from baseline, with the corresponding SE, can be plotted at each visit in the case results warrant further investigation. These parameters will be presented by the biological functions defined in Section 4.8.2. For glucose, only fasting samples will be included in the summaries.

Individual patient laboratory parameter measurements will be additionally evaluated by PCSV criteria (See Appendix 10.4), specifically identifying patients with at least one post-baseline measurement that meets the PCSV criteria within the respective TEAE periods. These laboratory parameters will be presented by the biological functions defined in Section 4.8.2. The incidence of PCSVs at any time during the respective TEAE periods will be summarized regardless of the baseline level, and again according to the following baseline categories:

- Normal (according to PCSV criterion/criteria)/missing
- Abnormal according to PCSV criterion or criteria

Patient listings of laboratory measurements that meet PCSV criteria will be provided for the report appendix. For those laboratory parameters that don't have an associated PCSV criteria,

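### SAP 10.4: the CLcr and eGFR PCSV rows list normal values as a PCSV band and have no band below 15

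*SAP*

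**What the plan says.** SAP 10.4 tabulates the PCSV criteria. The rows for CLcr (Cockcroft-Gault) and eGFR (MDRD) carry identical bands: 15 to <30 ("severe decrease in GFR"), 30 to <60 ("moderate decrease in GFR"), 60 to <90 (mild decrease) and 90 or more (labelled normal). Neither row has an entry below 15, and neither says that the top band is only a reference.

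SAP 5.8 states what a PCSV is: "PCSV values are defined as abnormal values considered medically important by the Sponsor according to predefined criteria/thresholds".

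SAP 5.8.3 applies the list by "identifying patients with at least one post-baseline measurement that meets the PCSV criteria within the respective TEAE periods". Incidence is then shown regardless of baseline and again by baseline status, normal or missing against "Abnormal according to PCSV criterion or criteria". SAP 6.3 puts a missing baseline in the normal/missing group.

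Protocol 6.2.3 (criterion 12) excludes "Estimated glomerular filtration rate <30 mL/min/1.73 m"² at screening, "according to 4-variable MDRD study equation (calculated by central lab").

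SAP 4.8.2 lists the renal parameters as creatinine, BUN and uric acid. CLcr and eGFR are not named there.

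**The concern.** A PCSV list should separate abnormal values from normal ones and should capture the most extreme values. These two rows do neither as printed: a normal value meets a listed criterion, and a value below 15 meets none. The baseline split in SAP 5.8.3 uses the same criterion, so a row whose bands include normal values also blurs who counts as normal at baseline.

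What is at stake is whether the two GFR rows of the safety tables can be read. Patients may enter with eGFR as low as 30 and up to age 80, and SAP 4.2 provides for chronic kidney disease and diabetes in the medical history. Those who start near 30 are the ones for whom a band below 15 could be needed.

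**Working it through.** No figure in the plan needs reproducing. The check assigns values to the printed bands and follows the counting rules.

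**1. Coverage.** The bands [15, 30), [30, 60), [60, 90) and [90, ∞) join without gaps and cover every value from 15 upward.

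| Value | Band in SAP 10.4 |
|---|---|
| 5, 10, 12, 14.9 | none |
| 15, 29.9 | severe decrease |
| 30, 59.9 | moderate decrease |
| 60, 89.9 | mild decrease |
| 90, 95, 120 | normal |

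**2. Bands merged into one criterion.** A patient meets it with any value of 15 or more. The screening floor for eGFR is 30, and 30 > 15, so essentially every patient is abnormal at baseline on the eGFR row. The normal/missing group then holds little but missing baselines. After baseline, every patient with at least one value of 15 or more is a case, including one stable at 95.

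**3. Each band as its own criterion.** This resembles the multi-threshold ALT and CPK rows. The 15 to <30 band is then informative, because patients below 30 were excluded at screening. But a patient who improves from 85 to 92 becomes a case in the top band with a baseline outside that band, and a value of 12 is still in no band.

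**4. Cover from the creatinine row.** Its criteria are ≥150 µmol/L, and ≥30% and ≥100% from baseline (taken as increases). The protocol names the 4-variable MDRD equation but does not print its coefficients. *Assumption:* the standard form, eGFR = c × Scr^(−1.154) × age^(−0.203) × 0.742 if female × 1.212 for the race factor, with c = 175 or 186, Scr in mg/dL and 88.4 µmol/L per mg/dL. Solving for eGFR = 15:

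- c = 175: creatinine 265 µmol/L (age 80, female, race factor 1) to 528 µmol/L (age 18, male, race factor 1.212).
- c = 186: 280 to 557 µmol/L for the same two patients.

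The whole range lies above 150 µmol/L. For relative change at fixed age:

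- Fall from 30 to 15: (30/15)^(1/1.154) = 1.82, a rise of about 82%, which meets the 30% criterion.
- Fall from 65 to 12: (65/12)^(1/1.154) = 4.32, a rise of about 332%, which meets both relative criteria.

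So under this assumption a fall in eGFR from 30 or more to below 15 is flagged on the creatinine row. The calculation was not repeated for CLcr.

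**The case against.** The strongest reply is that a PCSV is by definition abnormal, so a band labelled normal can only be a reference category and the bands are a classification. On that reading the normal-baseline group is not empty: it holds patients at 90 or more. This is a plausible intention, but the rows do not state it. ALT and AST are marked as distribution analyses, and these rows are not. It also leaves values below 15 unplaced.

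Second, the rows may never be used. SAP 5.8.3 presents laboratory results by the functions in SAP 4.8.2, which omits CLcr and eGFR. SAP 5.8 dates the PCSV list January 2009, and the list also carries orthostatic hypotension although Protocol 8.2.3.1 collects sitting blood pressure. This stands as a real uncertainty. It is a reason to settle whether the rows belong, not to leave them as printed.

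A reader might infer more than the documents support:

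- *No renal signal could be seen.* Creatinine has its own criteria, BUN has one (≥17 mmol/L), and SAP 5.8.3 summarises laboratory values by visit, including the maximum.
- *A patient in kidney failure is missed.* One qualifying post-baseline value is enough, so a declining patient still counts on these rows through any other value of 15 or more, though in a milder band. Only a patient whose every assessed post-baseline value is below 15 is absent from them.
- *Every patient is a PCSV case.* This needs the four bands to be merged, which the SAP does not instruct.
- *The lack of a baseline condition is an error.* BUN, sodium and platelets have none either, and SAP 5.8.3 handles baseline through the split.

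A line lost from the table cannot be fully excluded, but both rows lack the same band, while less-than entries for chloride, potassium and platelets are intact.

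**Conclusion.** The point holds for the CLcr and eGFR rows of SAP 10.4 as printed. They contradict the SAP's own definition of a PCSV by listing normal values, and they classify nothing below 15. The gap below 15 remains whether the bands are merged or read one by one; the statement that essentially all patients meet the criterion belongs to the merged reading only. That statement also rests on the screening eGFR limit, so it applies directly to the eGFR row. For CLcr, which has no entry limit, it assumes that hardly any enrolled patient starts below 15.

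The size is small: two rows of descriptive safety output, with no endpoint, test or error rate affected. The creatinine row, and possibly the BUN row, limits the consequence further. That reassurance rests on the MDRD coefficients assumed above.

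**What to change.** In SAP 10.4, for both CLcr and eGFR:

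- add a <15 band;
- state that 90 or more is the normal reference category and not a PCSV.

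The criterion is then any value below 90, graded in four bands. A value of 12 has a place, a value of 95 is not a case, and the SAP 5.8.3 split has a meaningful normal group (90 or more, or missing).

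Reconcile this with SAP 4.8.2, either by adding CLcr and eGFR to the renal parameters or by deleting the two rows from SAP 10.4.

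A table of worst post-baseline category by baseline category is optional. It would separate new from pre-existing impairment.

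The cost is SAP wording and minor table programming. Creatinine is already in the chemistry panel (Protocol 8.2.3.4), so no new tests are needed.

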10.5. Detailed Description of the Multiple Imputation Procedure

The following is a detailed description of the multiple imputation procedure which will be used for analysis of the secondary efficacy endpoints.

In general, the missing pattern is anticipated to be not monotone, a two-step approach will be used:

- Step 1: the MCMC method will be used in conjunction with the IMPUTE=MONOTONE option to create an imputed data set with a monotone missing pattern. Set the SEED=1643 option in SAS MI procedure
- Step 2: Using the monotone data set from step 1, missing data will be imputed using the regression method. Set the SEED=3461 option in SAS MI procedure

The imputation model for step 1 will include the treatment group and the values of the analyzed parameter at baseline and planned time-points up to week 24/week 16.

The imputation model for step 2 will include the same variables as in step 1 with the following additional variables:

- the randomization strata;
- age, BMI, and gender (age and BMI included as continuous variables).

Non-continuous variables included in the imputer's model (i.e., treatment group, randomization strata and gender) are not expected to be missing.

In addition, for continuous efficacy variables anticipated to have a non-normal distribution (i.e. TG and Lp(a)), data will be log-transformed before imputation process and then back-transformed to create the imputed data sets using the TRANSFORM statement of SAS MI procedure.

For variables other than those continuous efficacy variables anticipated to have a non-normal distribution (i.e. TG and Lp(a)), for each simulation leading to negative imputed value, another value will be redrawn using MINIMUM option of SAS MI procedure.

The number of imputations (100) will be informally verified by replicating sets of 100 imputations and checking whether the combined results are stable. If not stable, the number of imputations will be increased and informally checked as above, and thus continued until stable estimates are obtained.

10.6. Detailed Description of Pattern Mixture Model

As a sensitivity analysis of the primary efficacy endpoint (i.e. percent change from baseline to Week 16 in LDL-C), a pattern-mixture model approach will be used, with a different imputation strategy applied for missing LDL-C values during the on-treatment period (i.e. within the time period from the first double-blind study treatment administration up to the day of the last double-blind study treatment administration +35 days or to the day before the first open-label study treatment administration, whichever comes first for Group B or +14 days for Group A) and missing LDL-C values after treatment discontinuation (i.e. after the day of last study treatment

administration +35 days for Group B or +14 days for Group A) based on the following assumptions:

- Patients within 35 days for Group B or 14 days for Group A of their last study treatment administration would continue to show benefit from treatment similar to that observed at the scheduled time point. Therefore, LDL-C values missing during the on-treatment period will be considered “Missing at Random” and imputed using a model estimated using all samples collected on treatment.
- Patients who stopped taking their study treatment no longer benefited from it in the future, and thus tended to have LDL-C values returning to baseline. Thus LDL-C values missing after treatment discontinuation will be imputed based on patient’s own baseline value.

The assumptions for this approach are based on the following considerations:

- Missing values during the on-treatment period are mostly consecutive to:
 - Visits performed outside of the pre-specified time-window
 - No blood sample available although visit was done
 - LDL-C not measurable due to technical reasons

In addition, these missing data are often intermittent, i.e. followed by LDL-C values collected at subsequent visits. It is therefore considered reasonable to assume that these missing data were “At Random”.

Missing LDL-C values will be imputed 100 times to generate 100 complete data sets. The percent change from baseline to Week 16 will be derived from observed and imputed LDL-C at this time point. The completed data sets will be analyzed using an analysis of covariance (ANCOVA) model with treatment group and randomization strata as fixed effects, and the baseline LDL-C value as continuous covariate. The results from the 100 analyses will be combined using Rubin’s formulae. If necessary, the number of imputations (100) will be increased until stable estimates are obtained.

Imputation of missing data during the on-treatment period

Missing LDL-C values during the on-treatment period will be imputed from other on-treatment measurements assuming Missing At Random, using SAS® MI procedure.

Only LDL-C values collected during the on-treatment period will be included in the imputation model. This way, missing LDL-C values during the on-treatment period will be imputed based solely on observed on-treatment LDL-C values.

The imputation model will include the treatment arm, baseline LDL-C value, and all LDL-C values at pre-specified visits. Since the pattern of missing data will necessarily be non-monotone, a Monte-Carlo Markov Chain (MCMC) method will be used. A minimum value of 0 will be specified in order to avoid negative imputed LDL-C values.

A sample SAS code is provided below:

```
proc mi data=DATAIN out=DATAOUT nimpute=100 minimum=. 0 0 0 0 0 0 0 0 SEED=1643;
```

```
mcmc impute=monotone;  
var ARM LDL_BASE LDL_W2 LDL_W4 LDL_W8 LDL_W12 LDL_W16;  
run;
```

As stated above, the input dataset DATAIN will include only LDL-C values collected during the on-treatment period. Any LDL-C values collected during the post-treatment period will be excluded from the input dataset. In practice, the MI procedure will generate imputed values for all missing values (whether on-treatment or post-treatment), but only imputed values during the on-treatment period will be kept in the final datasets that will be analyzed using ANCOVA. Imputed values during the post-treatment period will be discarded and replaced by imputed values described in the next paragraph.

Imputation of missing data after treatment discontinuation

Missing LDL-C values during the post-treatment period will be imputed assuming LDL-C values would on average return to baseline values.

For each patient, missing post-treatment LDL-C values will be imputed 100 times, using a random draw from a normal distribution (SEED=3461), with mean equal to patient's own baseline value and variance equal to the conditional variance at the specific time-point, given the baseline value.

Let Y_0 and Y_1 denote the LDL-C at baseline and at the specific time-point respectively. Since Y_0 and Y_1 are assumed to have a bivariate normal distribution, the conditional variance of Y_1 given Y_0 is:

$$Var(Y_1|Y_0 = y_0) = \sigma_1^2(1 - \rho^2)$$

Where σ_1^2 denotes the variance of Y_1 and ρ the coefficient of correlation between Y_0 and Y_1 .

The conditional variance will be estimated from observed data within the same treatment arm at the specific time-point.

During the random generation process, a minimum value of 0 will also be applied in order to avoid negative imputed LDL-C values.

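### The sample code for the pattern-mixture analysis in SAP 10.6 does not do what the text of 10.6 says: as printed, a week-16 LDL-C value missing on treatment is never imputed

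*SAP*

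**What the plan says.** SAP 5.7.1.1 plans a pattern-mixture model as a check on the missing-at-random assumption behind the primary MMRM, and refers to Appendix 10.6 for the detail. Values missing on treatment are treated as missing at random. Values missing after the on-treatment period are drawn around the patient's own baseline. Each completed data set then goes into an ANCOVA of percent change at week 16.

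The text of 10.6 makes three commitments about the on-treatment part:

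- On-treatment gaps are to be "imputed using a model estimated using all samples collected on treatment".
- On the variables: "The imputation model will include the treatment arm, baseline LDL-C value, and all LDL-C values at pre-specified visits".
- On the result: "In practice, the MI procedure will generate imputed values for all missing values (whether on-treatment or post-treatment". Only the on-treatment imputations are kept, and 100 complete data sets result.

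The sample code that follows is one PROC MI call. Its imputation statement is "mcmc impute=monotone", its variable list is "var ARM LDL_BASE LDL_W2 LDL_W4 LDL_W8 LDL_W12 LDL_W16", and its MINIMUM list has one dot and eight zeros. No later step completes the on-treatment values.

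Appendix 10.5 describes the same option differently. There, "the MCMC method will be used in conjunction with the IMPUTE=MONOTONE option to create an imputed data set with a monotone missing pattern" is step 1 only, and a separate regression step imputes what is still missing.

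**The concern.** The two appendices cannot both be right about what the option delivers. If it only makes the pattern monotone, as 10.5 says, the call in 10.6 cannot give complete data. The values left unfilled are the ones this analysis needs, because the ANCOVA uses week 16 alone.

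The patients affected are those the SAP singles out for missing-at-random imputation: visits outside the window, samples not taken, and technical failures. If they drop out, that part of the pattern-mixture analysis becomes complete-case without saying so. Patients imputed around baseline then make up a slightly larger share of the arm. Nothing in the plan would flag this. A programmer has to depart either from the code or from the text, and the SAP does not say which governs.

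**Working it through.** No published figure is being reproduced. The check is a logical one, followed by counts.

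**1. Rule.** In a monotone completion, a missing value is filled only if a visit later in the variable list is observed. This matches the role that 10.5 gives the option.

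**2. Printed list.** There are five post-baseline visits (W2, W4, W8, W12, W16), with arm and baseline taken as observed. That gives 2^5 = 32 observed/missing patterns, of which 16 have week 16 missing.

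| Visit | Patterns with visit missing | Filled |
|---|---|---|
| W2 | 16 | 15 |
| W4 | 16 | 14 |
| W8 | 16 | 12 |
| W12 | 16 | 8 |
| W16 | 16 | 0 |

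Nothing follows week 16 in the list, so it is never filled. Full imputation, or a monotone fill plus a second step, would fill all 16. These are counts of possible patterns, not frequencies of patients.

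**3. Does the post-treatment step fill the gap?** No. The baseline-centred draws apply only to values missing after the on-treatment period.

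**4. Does adding the omitted earlier visits help?** No. With Group A's full list to week 16 (8 visits, 2^8 = 256 patterns), week 16 is missing in 128 and filled in 0. With Group B's list to week 16 (6 visits, 2^6 = 64 patterns), it is missing in 32 and filled in 0.

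**5. Does a visit after week 16 help?**
- Group A has none on treatment. The last dose is scheduled on day 106, the on-treatment period ends on day 106 + 14 = 120, and the next lipid visit is day 169.
- In Group B, a patient last dosed at week 16 is on treatment until day 113 + 35 = 148, so week 20 (day 141) falls inside. Adding week 20 would fill week 16 in 32 of 64 patterns, so it is only a partial cure.
- Week 24 is mostly unavailable. A patient last dosed on day 141 would reach day 141 + 35 = 176, but 10.6 cuts the period short, "to the day before the first open-label study treatment administration, whichever comes first for Group B". With open-label dosing on day 169 as scheduled, the period ends on day 168 and the day-169 sample lies outside it.

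**6. Visit list against text.** SAP 5.7.1 and the efficacy windows in 10.2 include week 6 for both groups and weeks 10 and 14 for Group A. The printed list has none of these.

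**7. MINIMUM against the variable list.** MINIMUM has 1 + 8 = 9 entries. The list has 7 variables: arm, baseline and five visits.

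**8. Illustrative size.** The documents give no missing-data rate. Assume that 2%, 5% or 10% of patients have week 16 missing on treatment:
- Group B: 108 × 0.02, 0.05 and 0.10 = about 2, 5 and 11 patients.
- Group A: 144 × 0.02, 0.05 and 0.10 = about 3, 7 and 14 patients.

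As printed, all of them would be left without a week-16 value.

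**The case against.** The code is introduced as a sample, and the text around it clearly requires complete data sets. On that view the plan is sound and one option in an example is wrong. Moreover, with 9 MINIMUM entries for 7 variables the call may not run unchanged (this was not tested in SAS), so someone would have to revise it and might notice the rest. This limits the likely harm but does not remove the conflict. The sample is the only operational specification of the on-treatment imputation, and the text credits the procedure with a result that 10.5 shows this option does not give.

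The second objection is that few values are at stake. The week-16 efficacy windows are wide (days 99 to 128 for Group B, 107 to 126 for Group A, against a scheduled day 113 ± 3), and SAP version 2 extended the Group B window by 2 days to reduce missing data. If missingness depends only on arm, baseline and strata, omitting these patients from an ANCOVA that adjusts for them mainly costs precision. This stands: no bias has been shown. The SAP also notes that "these missing data are often intermittent, i.e. followed by LDL-C values collected at subsequent visits". That helps at earlier visits, but not at week 16 when week 16 is the last variable listed.

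Third, the absence of week 20 for Group B is partly a matter of interpretation. The primary MMRM and the tipping-point analysis both stop at week 16, and the visits meant in 10.6 can be read the same way, although the reference to all on-treatment samples points the other way. It is a point to clarify, not a demonstrated error.

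**Conclusion.** The inconsistency is real and worth correcting. Followed literally, the 10.6 code leaves every on-treatment missing week-16 value unfilled, contrary to the text. This rests on how 10.5 describes the option and on the order of the printed list; it does not depend on any assumed missing rate. The visit omissions (week 6 for both groups, weeks 10 and 14 for Group A) and the MINIMUM mismatch are separate errors in the same call.

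The practical size is unknown and probably small. A reader might infer that the primary result, or the missing-data assessment as a whole, is compromised. The documents do not support that. The primary MMRM does not use this code, the tipping-point analysis uses the two-step method of 10.5, and the post-treatment draws around baseline are generated separately. Nor does the SAP plan a complete-case analysis: its text says the opposite, and the complete-case result arises only if the sample code is followed as it stands.

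**What to change.** Before database lock, make the code in 10.6 agree with its text.

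- **Completion.** Use IMPUTE=FULL, or keep MONOTONE and add an explicit regression step using the 10.6 model variables: arm, baseline and the LDL-C visits. Step 2 of 10.5 also includes strata, age, BMI and gender, so carrying it over unchanged would be a different imputation model. If those covariates are wanted, the 10.6 text should say so.
- **Variable lists.** Give one list per group, covering the scheduled LDL-C visits to week 16. Group A: W2, W4, W6, W8, W10, W12, W14, W16. Group B: W2, W4, W6, W8, W12, W16. State whether on-treatment week-20 values are also used for Group B. Leave out week 24, which would be almost entirely missing under the on-treatment cut-off.
- **MINIMUM.** Supply one entry for each variable in the corresponding list.
- **Post-treatment draws.** Keep them as described.

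The cost is a few lines of SAP text and code, with no effect on patients or data collection.
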